## Overview

The primary objective of this study is to examine whether the mindfulness mobile application engages adolescents and reduces rumination and subsequent psychopathology. We hypothesized that adolescents in the mindfulness intervention condition would experience a reduction in symptoms of depression, anxiety, and self-injury relative to those in the control group and that this would be accounted for by a reduction in the tendency to ruminate. We test this by using a randomized, controlled design, comparing the intervention group to a control group that uses the same mobile application for EMA but does not receive the mindfulness exercises.

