### **Sample**

We will recruit 150 adolescent girls and boys, ages 12-15. This age range was chosen to capture the developmental period directly preceding increased rates of depression (Hankin et al., 1998), providing an opportune window for prevention. Participants will be recruited through a recruitment letter mailed to students enrolled in grades 7-10 at a large, local, public school district with over 5000 students in our target age range. In order to maximize the potential of targeting the proposed mechanism, we will only enroll adolescents who report at least moderate baseline levels of trait rumination. This will be accomplished through a 2-question phone screen. Once parents verbally consent and the child has verbally assented, we will ask them to respond to two questions from the Children's Response Style Questionnaire (CRSQ; Abela, Brozina, & Haigh, 2002) that assess brooding, a particularly maladaptive aspect of rumination (Treynor, Gozalez, & Nolen-Hoeksema, 2003). The aggregate of these two questions are highly correlated with the full rumination subscale from the CRSQ ( $r = .79$ ,  $p < .01$ ) and have been associated with depressive symptoms and NSSI in previous work by the PI (Hilt et al., 2008). Adolescents who meet the screening criteria (age 12-15, score of 2 or higher on the brooding questions, and physically and cognitively able to use a mobile application) will be invited to participate in the study. Once they provide written consent and assent, they will be randomly assigned to a condition: EMA only or EMA + Mindfulness at a 1:1 ratio (i.e., ~ 75 participants per condition).

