### Questionnaires

At each time point (baseline, post, follow-up 1, follow-up 2), internalizing symptoms will be assessed using multiple informants (adolescent and parent). Additionally, adolescents will self-report on their self-injurious thoughts and behaviors, trait rumination, and trait mindfulness. Finally, parent-reported demographics will be obtained at baseline, and adolescent satisfaction with the application will be obtained at post. Questionnaires will take adolescents approximately 30 minutes to complete and less than 10 minutes for parents. Questionnaires will be completed online using Qualtrics (a survey software platform with secure data storage) except for the demographics form which will be completed on paper to avoid storing any identifying data on the server.

*Internalizing symptoms.* Depression will be assessed using the gold-standard, self-report Children's Depression Inventory (CDI; Kovacs, 1992). This 27-item questionnaire assesses behavioral, cognitive, and physical symptoms of depression and has high reliability and validity ( $\alpha=.88$ ). Anxiety will be assessed using the Multidimensional Anxiety Scale for Children (MASC; March, Parker, Sullivan, Stallings, & Connors, 1997), a 39-item reliable and valid index of anxiety in youth ( $\alpha=.88$ ). It yields a total score along with subscales for physical symptoms of anxiety, harm avoidance, social anxiety, and separation anxiety. Parent-reported internalizing symptoms will be assessed using the 5-item, internalizing subscale from the Pediatric Symptom Checklist (PSC; Jellinek & Murphy, 1988), a widely-used 35-item measure of psychopathology in youth with sound psychometric properties. All of these questionnaires have shown change in response to interventions in previous research.

*Self-injury.* Thoughts and behaviors related to suicide and NSSI will be assessed with the self-report form of the Self-injurious Thoughts and Behavior Interview (SITBI; Nock, Homberg, Photos, & Michel, 2007), a highly reliable and valid assessment tool used with adolescents.

*Rumination.* Trait rumination will be assessed with the rumination subscale from the CRSQ (Abela, Brozina, & Haigh, 2002). This 13-item subscale has demonstrated good reliability and validity ( $\alpha=.88$ ).

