**Specific Aim 2.** Testing of the hypothesis that the intervention will reduce symptoms through the mediating effect of reduced rumination will be accomplished by capitalizing on both trait-level questionnaire data and state-level EMA data. Using trait-level data, an indirect effect model will be tested to examine the effect of condition (EMA-only vs. EMA + Mindfulness) on each outcome (depressive symptoms, anxiety symptoms, parent-reported internalizing symptoms, and self-injury) through the indirect effect of rumination (see Figure 2). These analyses will be accomplished using the PROCESS macro (Hayes, 2013) for SPSS (IBM Corp.) which relies on bootstrapping to generate bias corrected confidence intervals. This approach is particularly well-suited for testing mediation models with relatively small sample sizes. It also allows for the addition of covariates and/or moderators if inclusion of them are warranted. For example, if there are sex differences in rumination and/or symptoms, as is likely based on previous research (e.g., Hilt, McLaughlin, & Nolen-Hoeksema, 2010), sex can be covaried or tested as a moderator of effects (**Exploratory Aim**) using methods described by Preacher, Rucker, and Hayes (2007). Dose can also be examined as a covariate, to test whether variability in use of the mobile application affects outcomes. These indirect effects models will be tested at each time period (post, follow-up 1, and follow-up 2). If the hypothesis is supported for

[figure not shown]

Figure 2. Conceptual indirect effect model. Note that moderators (e.g., sex) may also be included.

the post-intervention time period, it will be helpful to see if effects are maintained at 6 and 12 weeks. If the hypothesis is not supported at the post-intervention period, it will be possible to examine delayed effects at the follow-up time points. For example, the intervention could reduce rumination first and have a delayed effect on symptoms.

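### The planned trait-level mediation models cannot show that rumination falls before symptoms do; a lagged model on data already collected should be added

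*Combined protocol and SAP*

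**What the plan says.** The Overview states the objective as finding out whether the app "engages adolescents and reduces rumination and subsequent psychopathology", with the symptom change explained by a fall in rumination. That is a claim about sequence.

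The Questionnaires section supplies repeated measures: "At each time point (baseline, post, follow-up 1, follow-up 2), internalizing symptoms will be assessed". Its next sentence adds trait rumination and self-injury. From the Procedure section, post is at week 3, follow-up 1 six weeks later and follow-up 2 six weeks after that.

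Under Specific Aim 2, the SAP fits an indirect-effect model (condition, rumination, outcome) for each of four outcomes, using the PROCESS macro and bias-corrected bootstrap intervals. On timing it says: "These indirect effects models will be tested at each time period (post, follow-up 1, and follow-up 2"). Covariates are optional, and neither baseline rumination nor baseline symptoms is named. If post gives no support, the follow-ups may be searched for delayed effects, since "the intervention could reduce rumination first and have a delayed effect on symptoms". No model is written for that case.

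The SAP also allows state-level models of the momentary (EMA) ratings, including mood at later prompts and, conditionally, mediation by state rumination.

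**The concern.** Randomisation protects the paths that start at condition. It does not protect the path from rumination to symptoms. When both are measured in the same wave, their association is the same whether rumination drives symptoms, symptoms drive rumination, or something else moves both. A significant indirect effect then says that the data fit mediation; it does not say which came first.

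The SAP calls the mediation hypothesis its primary hypothesis. An app that improved mood directly, with rumination falling only because mood improved, could be reported as working through rumination. That conclusion could then shape the larger trial that the protocol has in view.

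**Working it through.** **Inputs.** From the Sample section: "We will recruit 150 adolescent girls and boys, ages 12-15", allocated "at a 1:1 ratio (i.e., ~ 75 participants per condition"), so 150 / 2 = 75 per arm. The documents give no effect size, SD, error rate or power for the mediation test, so there is no planned figure to reproduce. Every path value below is an assumption.

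**Which wave supplies rumination.** Baseline rumination precedes randomisation and cannot carry a randomised effect. The next measurement is at post. A post model therefore has to take rumination and symptoms from the same wave. For follow-up 1 and 2 the mediator's wave is unstated; same wave is the natural reading, not a stated fact.

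**What the models estimate under pure reverse causation.** Let X be condition, m rumination and y symptoms. Subscripts 0, 1 and 2 denote baseline, post and follow-up. Baseline variances are 1, the baseline correlation is 0.5 and residual variance is 0.36:
- y1 = 0.6·y0 − d·X + e
- m1 = 0.4·m0 + 0.5·y1 + e
- y2 = 0.6·y1 + e

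Rumination never affects symptoms. The within-arm variance of y1 is 0.36 + 0.36 = 0.72, so d = 0.3 or 0.5 is 0.35 or 0.59 SD. The effect of condition on rumination is a = −0.5d. The rumination coefficient b in each model is:
- Same wave, baseline scores adjusted: b = (0.5 × 0.36) / (0.25 × 0.36 + 0.36) = 0.18 / 0.45 = 0.40. So ab = −0.20d = −0.06 or −0.10 (simulated means −0.057, −0.097).
- Same wave, unadjusted: cov(m1, y1) = 0.4 × 0.30 + 0.5 × 0.72 = 0.48 and var(m1) = 0.16 + 0.18 + 0.36 + 0.12 = 0.82. So b = 0.585 and ab = −0.088 or −0.146 (simulated −0.081, −0.142).
- Lagged, unadjusted: b = 0.6 × 0.48 / 0.82 = 0.351 and ab = −0.053 or −0.088 (simulated −0.048, −0.086).
- Lagged, with m0, y0 and y1 in the outcome equation: b = 0 and ab = 0 (simulated 0.000).

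The first three models report mediation that does not exist. A lag without post symptoms does not cure it.

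**How often mediation is declared.** N = 150, 95% bias-corrected bootstrap interval (the plan's method) with 1000 resamples, 600 trials per cell, d = 0.3 / 0.5:

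| Model | Reverse causation | Both improve, shared same-wave factor, no causal link | True mediation, within and after three weeks |
|---|---|---|---|
| Same wave, unadjusted | 16% / 42% | 52% / 89% | 60% / 97% |
| Same wave, baseline adjusted | 28% / 64% | 72% / 98% | 88% / 100% |
| Lagged, unadjusted | 18% / 46% | 51% / 84% | 60% / 96% |
| Lagged, baseline and post symptoms adjusted | 2% / 5% | 7% / 7% | 89% / 100% |

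Monte Carlo error is at most 1.96 × √(0.25 / 600) = 4 points. Baseline adjustment raises the false rate. At N = 120 (an assumed 20% loss), the reverse-causation rates are 13% to 37% unadjusted, 25% to 57% baseline adjusted and 2% to 6% for the adjusted lagged model.

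**Sensitivity to the test and the paths.** Requiring both a and b to be significant (3000 trials, direct effects 0.3 to 0.5 SD, slopes 0.3 to 0.5), the baseline-adjusted same-wave post model gave 12% to 47% and the adjusted lagged model about 1% to 2%. At 0.8 SD the same-wave rates were 48% to 85% and the lagged rates 2% to 4%. A further run gave 8% to 39% against 0.5% to 2.5%.

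**What the lagged model costs.** If rumination acts only within the three weeks (a = 0.5, same-wave b = 0.3), the baseline-adjusted same-wave post model detected mediation in 77% to 93% of trials and the adjusted lagged model in 22% to 63%. A second run gave about 91% against 36% to 60%.

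**The case against.** Four points on the other side deserve weight.

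First, a reader might infer that every mediation model is same-wave, or that the trial cannot address order at all. The documents support neither. The mediator's wave at the follow-ups is not stated, and the delayed-effect sentence leaves room for post rumination followed by later symptoms. Rumination and symptoms are collected at all four waves, so the data can speak to order. What stands is that the post model is same-wave by necessity and that nothing lagged is prespecified. The delayed-effect look is triggered only when post fails, so a false positive at post would not trigger it.

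Second, Aim 2 also has the momentary data, including mood at later prompts. This helps a little. Those models are optional, their outcome is momentary mood rather than the four questionnaire outcomes, no lag from rumination to mood is stated, and the two are rated in the same set of questions.

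Third, it is tempting to say that same-wave models would largely miss a delayed effect. That depends on how stable rumination is. With a = 0.5 and lagged b = 0.3, the unadjusted same-wave follow-up 1 model detected 3%, 20%, 52% and 72% at stabilities of 0.3, 0.5, 0.7 and 0.85; the lagged model detected 86%, 90%, 89% and 65%. For a trait scale, high stability is plausible, so that argument is not relied on here.

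Fourth, the plan looks at post first and treats delay as the fallback, so early action is its leading scenario. There the adjusted lagged model is clearly weaker. This is a good reason not to discard the same-wave models.

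**Conclusion.** The concern holds for the trait-level models as planned. They do not fix temporal order or adjust for prior scores, and a positive result at post would not distinguish mediation from reverse causation. Under the assumed paths, with effects of 0.3 to 0.5, the false-mediation rate is roughly 8% to 64%, against about 0.5% to 5% for a lagged model adjusted for post symptoms. The direction of this contrast is the same in every simulation and follows from the algebra; the exact rates rest on assumed stabilities, slopes and effects, none of which the documents give.

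This should be fixed, but it does not undermine the trial. The randomised comparisons of condition on rumination and on symptoms are untouched. What is at risk is the mechanism claim, and in particular the word subsequent in the objective.

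**What to change.** In Specific Aim 2 of the SAP:
- State the wave that supplies rumination in every trait-level model.
- Keep the same-wave models, and describe a positive result as consistent with mediation but not as evidence of direction.
- Add a prespecified lagged model: condition, then trait rumination at post, then symptoms at follow-up 1 (and at follow-up 2). Put baseline rumination and baseline symptoms in both equations, and post symptoms in the outcome equation only.
- Rest any claim that reduced rumination precedes symptom reduction on the lagged model.

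The change is SAP wording; no new data are needed. The SAP should also state the limits. The lagged model depends on follow-up attendance. It discards any effect already passed on by post, so detection may be about 20% to 60% where the same-wave post model would reach about 77% to 93%. It does not remove unmeasured confounding between rumination and symptoms.

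### The plan intends to look at whether effects are maintained or delayed, but tests each wave separately and never estimates how the effect changes between waves

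*Combined protocol and SAP*

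**What the plan says.** Under Specific Aim 2 of the Statistical Analysis Plan, the trait-level analysis examines the effect of condition on "each outcome (depressive symptoms, anxiety symptoms, parent-reported internalizing symptoms, and self-injury) through the indirect effect of rumination". It uses a macro "which relies on bootstrapping to generate bias corrected confidence intervals". On timing, the plan says: "These indirect effects models will be tested at each time period (post, follow-up 1, and follow-up 2".

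It then branches on the post result. If the hypothesis is supported there, "it will be helpful to see if effects are maintained at 6 and 12 weeks". If it is not, "If the hypothesis is not supported at the post-intervention period, it will be possible to examine delayed effects at the follow-up time points". As an example of delay it offers rumination falling first and symptoms following later.

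Two other parts of the document might have supplied a test of change, and neither does:

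- The multilevel models (Aims of the study and significance; the later part of Specific Aim 2) concern momentary app data and links from state to trait. They do not model the questionnaire outcomes across the three post-baseline waves.
- The promise to correct for multiple testing (end of Specific Aim 1) governs false positives within a family of tests. It creates no contrast between waves.

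The document does not state an effect size, power, alpha, dropout rate, correlation between waves, or criterion for calling an effect maintained or delayed.

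**The concern.** Maintenance, fading and delayed onset are statements about how an effect differs between two times. The plan estimates the effect at each time but not that difference. Two estimates of the same true effect can fall on opposite sides of a significance threshold through sampling error alone.

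This problem is distinct from multiplicity. It remains with a single outcome and a corrected alpha. Correction lowers the power at each wave, which moves the chance of a spurious pattern up or down but does not remove it.

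At stake is the reading of the 12-week follow-up: a report could say that benefit wore off, or emerged late, when the data cannot tell either from a constant effect. The indirect-effect estimate at any one wave is not affected by this point.

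**Working it through.** The plan gives no figure to reproduce. The question is how often a truly constant effect would show a faded or delayed pattern if labels follow significance.

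**Inputs from the document (Sample; Specific Aim 2).** Sample size: "We will recruit 150 adolescent girls and boys, ages 12-15". Allocation: "EMA only or EMA + Mindfulness at a 1:1 ratio (i.e., ~ 75 participants per condition". Three post-baseline waves, one model per wave.

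**Assumptions, because the document is silent.** Two-sided alpha 0.05; the same true effect at all waves; three normal test statistics with equal mean and equal pairwise correlation ρ; per-wave power 30% to 95%; ρ from 0.3 to 0.8.

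**Step 1: plausible power per wave.** For a two-group comparison with n = 75 per arm and no baseline adjustment, power ≈ Φ(d√(n/2) − 1.96), with √(75/2) = 6.124.

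| d | d × 6.124 | Power |
|---|---|---|
| 0.2 | 1.22 | 23% |
| 0.3 | 1.84 | 45% |
| 0.4 | 2.45 | 69% |
| 0.5 | 3.06 | 86% |
| 0.6 | 3.67 | 96% |

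**Step 2: broad labelling rule.** Faded means significant at post but not at both follow-ups. Delayed means not significant at post but significant at one or more follow-ups. Then

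rate = 1 − P(all three significant) − P(none significant).

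At 50% power both probabilities equal 1/8 + 3·arcsin(ρ)/(4π), so the rate can be checked by hand:

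- ρ = 0.3: 1 − 2 × 0.1977 = 0.6046, about 60%
- ρ = 0.5: 1 − 2 × 0.2500 = 50%
- ρ = 0.7: 1 − 2 × 0.3101 = 38%

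Other power levels were simulated (1,000,000 draws per cell):

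| Power per wave | ρ = 0.3 | ρ = 0.5 | ρ = 0.7 | ρ = 0.8 |
|---|---|---|---|---|
| 30% | 52% | 43% | 33% | 27% |
| 50% | 60% | 50% | 38% | 31% |
| 70% | 52% | 43% | 33% | 27% |
| 80% | 40% | 34% | 26% | 21% |
| 90% | 24% | 20% | 16% | 13% |
| 95% | 13% | 11% | 9% | 8% |

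**Step 3: stricter rule.** Suppose both follow-ups must disagree with post. Six of the eight significance patterns are mixed: three with one significant wave and three with two. Under equal correlation, patterns with the same number of significant waves are equally likely. The strict rule counts one of each three, so its rate is one third of the broad rate: 60/3 = 20% at most and 8/3 ≈ 3% at least.

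**Step 4: cross-check on the indirect effect.** Full mediation data were simulated with constant paths: condition to rumination a, rumination to symptoms 0.5, 75 per arm, 1,500 trials per cell. A Monte Carlo interval stood in for the bootstrap. Broad-rule rates at between-wave correlation 0.5 / 0.7 / 0.8 of the simulated data were:

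- a = 0.3: 50 / 37 / 31%
- a = 0.4: 45 / 34 / 29%
- a = 0.5: 29 / 19 / 15%
- a = 0.6: 12 / 8 / 5%

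These agree with Step 2 at matching power, allowing a few points of simulation noise.

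**Step 5: a direct test of change.** With a constant effect, a joint condition-by-wave test at 0.05 signalled change in 5.4%, 4.9% and 5.2% of simulated trials (d = 0.3 and 0.4 with ρ = 0.7; d = 0.5 with ρ = 0.5). This was done for the total effect, not for a contrast of indirect effects.

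**The case against.** The strongest reply is that the plan does not commit itself to labelling by significance. Its sentences on maintenance and delay are permissive, and only the entry condition (supported or not at post) is explicit. Each model also yields a confidence interval, so the authors could compare estimates. The first part stands: the labelling rule is implied, not stated. The second helps only in part. The three estimates come from the same participants, so single-wave intervals do not give the interval for their difference.

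A reader might infer that this trial would misread a constant effect in a third to almost half of cases. The documents do not support that as a general statement. That figure needs per-wave power of about 30% to 70%, correlation of about 0.5 to 0.7, and a rule under which one disagreeing follow-up is enough. At 90% power the broad-rule rate is 13% to 24% across the correlations tabulated. Baseline adjustment, which the plan does not specify, would raise power and lower the residual correlation. Dropout or a multiplicity correction would lower power. The rates are also per outcome.

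It is also fair to say that the plan's own example of delay is a lag from rumination to symptoms. A condition-by-wave term does not test that directly, so such a term alone would not be an adequate remedy.

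Finally, the study is presented as a potential proof of concept. That limits the weight of the point but does not supply the missing contrast.

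**Conclusion.** The concern holds in this form: the plan raises maintenance and delay as questions, approaches them through separate wave-by-wave tests, and provides neither an estimate of change between waves nor a criterion for the labels.

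The size is conditional on labelling by significance, a constant true effect, three waves and two-sided alpha 0.05. It is about 33% to 50% in the middle of the plausible range under the broad rule, about 8% to 60% over the full grid, and about 3% to 20% if both follow-ups must disagree with post. None of these is a property of the trial that can be read from the documents. The structural gap does not depend on them. The point should be settled before analysis; it does not invalidate the wave-specific analyses.

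**What to change.** Keep the wave-specific estimates and add the following to the Statistical Analysis Plan:

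1. **Condition effect over time.** For each outcome, fit one longitudinal model of the three post-baseline waves with condition, wave, condition × wave and the baseline value. Use a link suited to the outcome for self-injury.
2. **Indirect effect over time.** The model in item 1 contains no mediator, so it cannot compare indirect effects. Fit a longitudinal mediation model in Mplus, which the plan already uses, or bootstrap participants jointly across waves. Take rumination as mediator with its baseline value as covariate, and include a lagged path from post rumination to follow-up symptoms.
3. **Reporting.** Give the post-to-follow-up differences in the condition effect and in the indirect effect with 95% intervals.
4. **Wording rule.** Claim fading or delay only when the interval for the relevant difference, or for the lagged effect, excludes zero. For maintenance, report the follow-up estimate and the interval for the change, and do not infer it from a non-significant difference. Otherwise state that the time course is undetermined.

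The cost is plan wording and additional models on questionnaire data already scheduled at every wave. The drawback is that the contrast will often be inconclusive. Its standard error relative to a single-wave effect is √(2(1 − ρ)): √0.6 ≈ 0.77 at ρ = 0.7 and √1.2 ≈ 1.10 at ρ = 0.4. For example, an effect with 70% power at post has an expected z of 1.96 + 0.52 = 2.48. If it halved by follow-up, the contrast would have expected z of 1.24/1.10 = 1.13 to 1.24/0.77 = 1.61, giving power of about Φ(−0.83) = 20% to Φ(−0.35) = 36%. The report must then say that the question is open.
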